### **11.1.** Safety and Efficacy Assessments

The safety and efficacy of APL-9 treatment will be assessed by objective endpoints and compared between treatment groups. These endpoints relate to AEs, overall hospitalization, use of mechanical ventilation and oxygen, assessments of organ failure, and overall survival. The SoA (Table 1) provides details of the scheduling of these assessments.

Assessments to be performed during the study are described below and in the SoA (Table 1). Every effort should be made to ensure that the protocol-required assessments are completed as described.

If deemed necessary, additional safety measurements will be performed at the discretion of the investigator.

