### 12.3.2. Analysis of Secondary Efficacy Endpoints

Continuous variables will be summarized using descriptive statistics (eg, median and mean); for categorical variables, the frequency and percentage in each category will be displayed. Time-to-event data (such as time to hospital discharge and time to mechanical ventilation discontinuation) will be summarized using Kaplan-Meier estimates accounting for censored observations (and analyzed using the Cox proportional hazard model if appropriate).

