2.1.2 Secondary Objectives

The secondary objectives of this study are to evaluate the effect of APL-9 on:

- Hospital length of stay
- Overall survival
- Change in Sequential Organ Failure Assessment (SOFA) score
- Time on mechanical ventilation
- Time on oxygen therapy (i.e., time on mechanical ventilation or supplemental oxygen therapy)
- APL-9 pharmacokinetics (PK)
- APL9 pharmacodynamics (PD; the effect of APL9 on complement, and inflammation biomarkers)

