5.2 Demographics and Baseline Characteristics

Demographics and baseline characteristics will be summarized for safety set including:

- Age at screening (years)
 If not collected, then it will be calculated as (year of informed consent form signed birth year)
- Age in categories (<65 years and ≥ 65 years)
- Sex, Childbearing Potential, Race, Ethnicity
- Baseline Weight (kg), Height (cm), Body Mass Index (BMI, kg/m²)
- Randomization Stratification Factors (Part 2 Only)
- Baseline use of mechanical ventilation, Baseline use of supplemental oxygen
- Baseline Respiratory Rate, Oxygen Saturations, Temperature, Blood Pressure (Systolic and Diastolic), Heart Rate
- Baseline Level of Consciousness
- Baseline Sequential Organ Failure Assessment (SOFA) score

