6. EFFICACY ANALYSIS

All efficacy analyses will be summarized for each study part. Efficacy data will also be analyzed by treatment group in Part 2. Hypothesis testing will be performed for part 2 between two treatment groups.

Unless otherwise specified, baseline for all efficacy analyses is defined as the last non-missing measurement recorded prior to taking the first dose of study drug.

All CIs will be presented as 2-sided 90% and/or 95% CIs. All statistical tests will be 2-sided hypothesis tests performed at the 10% level of significance.

The primary efficacy analyses will be performed for full analysis set (FAS). The supportive efficacy analyses will be performed for Intent-to-Treat (ITT) set.

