6.2.2 Sequential Organ Failure Assessment (SOFA) score

Organ failure status will be assessed using the SOFA score (see Table 1), which assesses 6 organ systems: respiration, coagulation, liver, cardiovascular, central nervous system, and renal (Ferreira et al., 2001). A subject will be defined as being free of organ failure when the SOFA score is zero. The SOFA score will be assessed at baseline on Day 1 and as listed in the schedule of assessment (SOA), based on worst daily values. SOFA score at each assessment and changes from baseline over time will be summarized using descriptive statistics.

Table 1: Sequential Organ Failure Assessment (SOFA) Scoring

Variables	0	1	2	3	4	
Respiration						
PaO ₂ /FiO ₂ , mmHg	>400	≤400	≤300	≤200ª	≤100a	
or SpO ₂ /FiO ₂ , mmHg	≥512	≥357 to <512	≥214 to <357	≥89 to <214	<89	
Coagulation						
$Platelets \times 10^3/\mu L$	>150	≤150	≤100	≤50	≤20	
Liver						
Bilirubin, mg/dL ^b <1.2		1.2 -1.9	2.0 -5.9	6.0 -11.9	>12.0	
Cardiovascular						

Hypotension	No hypotension	MAP <70 mm Hg	Dopamine ≤5 or dobutamine (any dose) ^c	Dopamine >5, epinephrine ≤0.1, or norepinephrine ≤0.1°	Dopamine >15, epinephrine >0.1, or norepinephrine >0.1 ^c	
Central nervous system						
Glasgow Coma Scale score ^{d,e}	15	13 -14	10 -12	6 -9	<6	
Renal						
Creatinine, mg/dL or urine output (mL/d) ^f	<1.2	1.2 to 1.9	2.0 to 3.4	3.5 to 4.9 or <500	>5.0 or <200	

Abbreviations: FiO2 = fraction of inspired oxygen; MAP = mean arterial pressure.

- 5 Seems able to talk
- 3 Questionable ability to talk
- 1 Generally unresponsive

Source: Ferreira et al. 2001.

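### SOFA change is a secondary objective, but the SAP prespecifies no between-arm SOFA estimate, interval or baseline-adjusted model for Part 2

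*SAP*

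**What the plan says.** SAP 2.1.2 lists "Change in Sequential Organ Failure Assessment (SOFA) score" among the effects of APL-9 to be evaluated; protocol 6.1.2 has the same objective. Protocol 11.1 sets the intent: "The safety and efficacy of APL-9 treatment will be assessed by objective endpoints and compared between treatment groups". It names organ failure assessments among those endpoints.

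The lead-in to SAP 6 covers all efficacy endpoints: "Efficacy data will also be analyzed by treatment group in Part 2", and "Hypothesis testing will be performed for part 2 between two treatment groups". It sets two-sided tests at 10% and intervals at 90% and/or 95%.

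SAP 6.2.2, the only SOFA analysis section, then plans this: "SOFA score at each assessment and changes from baseline over time will be summarized using descriptive statistics". That agrees with protocol 12.3.2, which says of continuous secondary variables: "Continuous variables will be summarized using descriptive statistics (eg, median and mean".

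Baseline SOFA is available. SAP 5.2 lists "Baseline Sequential Organ Failure Assessment (SOFA) score" among the characteristics to be summarized, and protocol Table 1 schedules SOFA at baseline, Days 3, 5, 7, 11 and 15, and end of treatment or discharge. The stratification factors in SAP 3.3 are need of mechanical ventilation and age group, not SOFA.

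**The concern.** The plan states an objective about an effect, says arms will be compared, and promises tests and intervals, but gives SOFA no method that would produce a comparison. No test, model, contrast, main visit or covariate is named for it. The other efficacy endpoints are treated differently. SAP 6.2.1 gives the time-to-event endpoints log-rank tests and a Cox model with the stratification factors and a 90% CI. SAP 6.3.1 gives even the exploratory viral endpoint a named between-arm test. SAP 14.2 records that the stratified test and Cox model were added in this version, but nothing similar was added for SOFA.

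Two things are at stake. First, the general promise of testing has no SOFA method attached, so the visit and the method could be chosen after the data are seen. Second, with about 30 subjects per arm, a chance difference in baseline SOFA feeds into any raw comparison, and the baseline measurement that could remove it is not used in a model.

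**Working it through.** **1. The plan's own figure.** The only sample-size figures are the chances of seeing at least one SAE with about 30 per arm (protocol 12.1, SAP 3.2). From 1 − (1 − p)^30, true incidences of 1%, 4%, 7% and 10% give 26.0%, 70.6%, 88.7% and 95.8%, against the stated 26%, 71%, 89% and more than 95%. They reproduce. They say nothing about SOFA, but they confirm n = 30 per arm as the working number.

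**2. Inputs for SOFA precision.** n = 30 per arm and a 90% interval come from the documents. The SOFA SD and the baseline-to-visit correlation ρ are not given. I assume equal SDs at baseline and follow-up, and ρ of 0.3, 0.5 or 0.7.

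**3. Formulas.** At one visit, the variance of the between-arm difference is SD² × 2f/n, where f is:
- observed score: 1
- change from baseline: 2(1 − ρ)
- ANCOVA on baseline: 1 − ρ²

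The 90% half-width is 1.645 × SD × √(2f/n). For the observed score this is 1.645 × √(2/30) = 0.425 SD.

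**4. Results.** SAP 6.2.2 tabulates both the score and the change, so the fair comparator is whichever of the two has the smaller variance. Each cell gives f, then the half-width in SD units.

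| ρ | Score | Change | ANCOVA | ANCOVA ÷ better summary | Equivalent extra subjects |
|---|---|---|---|---|---|
| 0.3 | 1; 0.425 | 1.40; 0.503 | 0.91; 0.405 | 0.91/1 = 0.91 | 1/0.91 − 1 = 10% |
| 0.5 | 1; 0.425 | 1.00; 0.425 | 0.75; 0.368 | 0.75/1 = 0.75 | 1/0.75 − 1 = 33% |
| 0.7 | 1; 0.425 | 0.60; 0.329 | 0.51; 0.303 | 0.51/0.60 = 0.85 | 1/0.85 − 1 = 18% |

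The interval narrows by the square root of the ratio: about 5%, 13% and 8%. In points, at ρ = 0.5 and an assumed SD of 3, the standard error falls from 3 × √(2/30) = 0.775 to 0.775 × √0.75 = 0.671. It scales with the SD: 0.516 to 0.447 at SD 2, and 1.033 to 0.894 at SD 4.

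**5. Chance baseline imbalance.** If the arms differ by d at baseline, the expected shift is ρd in the raw score difference and −(1 − ρ)d in the raw change difference; ANCOVA removes it under a linear relation. Ignoring stratification, one standard error of imbalance is √(2/30) = 0.258 SD. At ρ = 0.3 that shifts the change comparison by 0.7 × 0.258 = 0.18 SD; at ρ = 0.7 the shift is 0.3 × 0.258 = 0.08 SD.

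**6. Who is in the comparison.** Follow-up after discharge is by telephone (protocol 7.1), so later visits hold only subjects still alive and assessed. This selection affects the planned descriptive means and an ANCOVA alike. It also makes the real n at a visit smaller than 30 per arm; at 29 per arm the half-widths are already about 2% wider.

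**The case against.** The strongest defence is that descriptive analysis was a deliberate choice. Protocol 12.3.2 states it, the study is Phase 1/2 with a safety primary endpoint and no primary efficacy endpoint, and the pharmacodynamic objective in the same list is also handled descriptively. That stands, and it rules out calling for a confirmatory test. It does not settle the matter: the SAP states that it supersedes the protocol's analysis plan, and its own section 6 promises comparisons that 6.2.2 does not deliver.

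A reader might infer several stronger things that the documents do not support:
- That the objective goes unanswered. It is answered descriptively, by arm; what is missing is a prespecified estimate with an interval.
- That the comparison has no error bar at all. SAP 12.1 requires n, mean and SD, so a crude unadjusted interval can be worked out. The adjusted estimate cannot be recovered from those tables.
- That baseline is ignored. Change from baseline is tabulated, baseline SOFA is shown, and stratifying on ventilation plausibly balances part of baseline severity.
- That ANCOVA is worth up to 54% more subjects. That figure (1/0.65 − 1, at ρ = 0.3) compares it with the change score alone; the observed score is also reported and is the better summary there.

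It is also fair to say that an interval from assessed subjects only could lend false precision to a selected comparison. That stands as a condition on the fix. It is no reason to omit the estimate, because the planned means carry the same selection.

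**Conclusion.** The point holds as a worthwhile improvement. The Part 2 plan gives SOFA no between-arm estimate, interval or baseline-adjusted model, and this does not match the objective, protocol 11.1 or the lead-in to SAP 6. That conclusion needs no assumption.

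The precision gain does. With equal variances and ρ between 0.3 and 0.7 it is worth roughly 10% to 33% more subjects against the better planned summary. The formulas ignore the few degrees of freedom spent on covariates and take all 30 per arm as assessed at the visit. SOFA remains unpowered, and nothing here affects the primary safety analysis.

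**What to change.** In SAP 6.2.2, for Part 2, add an ANCOVA of SOFA at one prespecified visit, with treatment, baseline SOFA and the two randomization factors. Day 7 is a reasonable example, since it is a scheduled SOFA visit and comes before any treatment extension; the documents do not themselves designate a main visit. Report the adjusted mean difference with its 90% CI, labelled as an estimate and not a confirmatory test. Keep the descriptive tables.

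In the same paragraph, state how subjects who died or were discharged before that visit are handled, and add a sensitivity analysis, for example with deaths given the worst score (6 organ systems × 4 = 24).

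The cost is SAP wording, one extra model and a few degrees of freedom, with no new data. The real work is agreeing the rule for deaths and discharges, which the descriptive tables need as well.

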- b Fully eligible subjects can have screening assessments on the same day as baseline, which is defined as the day of initial study drug treatment.
- c Confirmation of SARS-CoV-2 infection may be completed more than 7 days before baseline. Presence of SARS-CoV-2 viral RNA or viral antigen may be detected in respiratory specimens (collected using nasopharyngeal or oropharyngeal swabs) with a qualitative nucleic acid amplification test (such as reverse transcriptase polymerase chain reaction), viral antigen test, or other diagnostic method that is authorized, cleared, or approved by the US Food and Drug Administration or equivalent authority for SARS-CoV-2 viral detection. Note: Serology-based antibody tests do not detect presence of virus and therefore are not considered diagnostic for active infection and cannot be used for study eligibility screening or for subsequent SARS-CoV-2 assessments.
- d Height/weight can be by subject assertion.
- e Discharged subjects who are followed up by phone will be provided with emergency study cards that include a list of symptoms associated with infections. The study card also guides subjects with instructions to contact their study physicians or seek emergency medical care if they experience any of the listed symptoms.
- f For continuous variables, the worst observed daily value will be recorded. Vital signs and ECG must be collected between the administration of the loading dose of study treatment and the initiation of the maintenance dose.
- g SOFA score variables (PaO2/FiO2 ratio or SpO2/FiO2 ratio, platelets, bilirubin, hypotension/vasopressor use, GCS score, creatinine) are detailed in Section 11.1.1 and Appendix 1.
- h A list of laboratory assessments is provided in Section 11.1.8. Blood will be collected 3 times on Day 1: (1) once prior to administration of the APL-9 bolus, (2) once as soon as possible following the bolus (within 5-10 minutes) prior to the continuous infusion, and (3) once at 2 hours after the beginning of the continuous infusion. Following that, assessments should be collected within the time frame of each calendar day. The use of silica reagents in coagulation panels should be avoided in subjects treated with APL-9.

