# 8.2. Subject Exclusion Criteria (Part 1 and Part 2)

Subjects are excluded from the study if any of the following criteria apply:

1. Female subjects being pregnant or breastfeeding

- 2. Active bacterial, fungal, or parasitic infection
- 3. History of neuromuscular degenerative disease (eg, amyotrophic lateral sclerosis, Duchenne muscular dystrophy, or multiple sclerosis)
- 4. Current participation in a clinical study with an investigational drug or biologic. NOTE: Participation in studies with the following therapies is NOT excluded:
  - a. Therapies approved (indicated) for COVID-19 by the applicable health authority
  - b. Therapies with emergency use authorization for COVID-19 by the US Food and Drug Administration or equivalent authorization by the applicable health authority
  - c. Therapies approved (indicated) by the applicable health authority and used for COVID-19 as part of standard care
- 5. Treatment with immune checkpoint inhibitors or other immunomodulators within 3 months prior to study enrollment (however, treatment with convalescent plasma, steroids, IL-6 inhibitors, and antiviral agents is NOT excluded)
- 6. Subjects who have, at screening, been on mechanical ventilation for >7 days
- Evidence of kidney failure AND liver failure at screening (estimated glomerular filtration rate <45 mL/min/1.73 m^2 and alanine aminotransferase level >5× the upper limit of normal, as assessed by the local laboratory)
- 8. Subjects with a hereditary complement deficiency

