#### 11.1.1. SOFA Score

Organ failure status will be assessed using the SOFA score, which assesses 6 organ systems: respiration, coagulation, liver, cardiovascular, central nervous system, and renal (Ferreira et al. 2001). A subject will be defined as being free of organ failure when the SOFA score is zero. The score will be assessed at baseline on Day 1 and as listed in the SoA based on worst daily values.

The SOFA score variables to be assessed are:

- PaO2/FiO2 ratio (mm Hg) or SpO2/FiO2 ratio—collected and entered into the database locally (see calculation instructions in Appendix 1)
- Platelets  $\times 10^3/\mu$ L—based on data provided by the local laboratory
- Bilirubin ( $\mu$ mol/L or mg/dL)—based on data provided by the local laboratory
- Hypotension/use of vasopressors—collected and entered into the database locally
- Glasgow Coma Scale score—collected and entered into the database locally (see Appendix 2)
- Creatinine (µmol/L or mg/dL)—based on data provided by the local laboratory

See Appendix 1 for additional information on calculating the SOFA score.

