#### 11.1.8. Clinical Laboratory Tests

Laboratory test samples (Table 2) are to be obtained at designated visits as detailed in the SoA (Table 1). Blood will be collected 3 times on Day 1: (1) once prior to administration of the APL-9 bolus, (2) once as soon as possible following the bolus (within 5-10 minutes) prior to the continuous infusion, and (3) once at 2 hours after the beginning of the continuous infusion. Following that, assessments should be collected within the time frame of each calendar day.

Blood samples will be analyzed at one or more central (or local) laboratory facilities, as defined in the laboratory manual. All laboratory reports must be reviewed, signed, and dated by the investigator. A legible copy of all reports must be filed with both the subject's eCRF and medical record (source document) for that visit. Any laboratory test result considered by the investigator to be clinically significant should be considered an AE (clinically significant AEs include those that at minimum require an intervention). Clinically significant abnormal values occurring during the study will be followed up until repeat test results return to normal, stabilize, or are no longer clinically significant.

Instructions for collection, handling, processing, storage, and shipping of samples will be provided in a separate laboratory reference manual prior to study initiation.

PARAMETERS ANALYZED AT	THE LOCAL LABORATORY	
Blood/serum/plasma samples		
Hematology	Serum chemistry	
ABG	Albumin	Ferritin
Hb	ALT	Glucose
Hematocrit	ALP	Haptoglobin
Platelet count	AST	HDL
RBC count	Bicarbonate	Iron
Reticulocyte count	Bilirubin (total, direct, and indirect)	LDH
Schistocytes	BUN	LDL
WBC count with differential	C-reactive protein (CRP)	Phosphorus
	C3 and C4	Potassium
Coagulation panel a	Calcium	Pregnancy
D-dimer	Chloride	Sodium
Fibrinogen	Creatinine	Total cholesterol
INR	Creatine kinase	Total protein
PT	Cystatin C	Triglycerides
	eGFR	Troponin
		Uric acid
Urine samples		
Urinalysis		
Bilirubin		Nitrite
Blood		pН
Glucose		Protein
Ketones		Specific gravity
Leukocyte esterase		Urobilinogen
-	sediment, including for presence of	
	performed on all abnormal urinalyses	
Respiratory swab	· · · · · ·	
Viral RNA or viral antigen assessme	nt	
SARS-CoV-2		
PARAMETERS ANALYZED AT	CENTRAL/SPECIALTY LABORATO	RIES
Plasma samples		
Complement biomarkers	Inflammation biomarkers CC	
Bb, C3a, C4a, C5a, TCC	TNFα	
	IL-1β	
	IL-6	
Serum samples		
PK concentrations		
AH50		

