6.3 Analysis of Exploratory Endpoints

6.3.1 Presence of active SARS-CoV-2 infection on at the end-of-treatment visit

Viral RNA assessment will be performed at the end-of-treatment visit. In the case where viral RNA assessment data is unavailable or patient died during the study, that subject will be treated as having a positive viral RNA test result. Fisher exact and/or chi-square test will be used to compare the proportion of subjects who have negative viral RNA test result between two treatment groups.

6.3.2 Incidence, duration, and extent of new oxygen therapy use (re-initiation 24 hours or more after cessation of prior oxygen therapy)

The number and percentage of patients reporting new oxygen therapy use (i.e., mechanical ventilation or supplemental oxygen therapy) as well as types of new oxygen therapy use will be tabulated by treatment groups. The duration of new oxygen therapy use will be calculated from the re-initiation of oxygen therapy use. For subjects with death of any cause or withdrawal of study participation after the re-initiation of oxygen therapy use, the duration of new oxygen therapy use will be imputed with the longest duration observed in the study. The duration of new oxygen therapy use will be presented by descriptive statistics.

6.3.3 Incidence, duration, and extent of new mechanical ventilation use (re-initiation 24 hours or more after cessation of prior mechanical ventilation)

The number and percentage of patients reporting new mechanical ventilation use, and types of new mechanical ventilation use will be tabulated by treatment groups. The duration of new mechanical

^a Values are with respiratory support

^b To convert bilirubin from mg/dL to μmol/L, multiply by 17.1

^c Adrenergic agents administered for at least 1 hour (doses are given in µg/kg/min).

^d For subjects who are intubated, the verbal response is scored as:

^e For subjects who are sedated, use an estimated score for Glasgow Coma Scale (the assumption is 15, if no other factors than sedation affect Glasgow Coma Scale score).

f To convert creatinine from mg/dL to μmol/L, multiply by 88.4

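### The SOFA tables score the renal item on creatinine or urine output, but the variable lists name creatinine only and no rule covers dialysis, so starting dialysis after baseline can register as renal improvement.

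*SAP*

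**What the plan says.** Change in SOFA is a secondary objective and SOFA score a secondary endpoint in both documents. The renal row of SAP Table 1, identical in protocol Table 5, is labelled "Creatinine, mg/dL or urine output (mL/d"). Its score-3 cell reads "3.5 to 4.9 or <500", and score 4 is creatinine above 5.0 mg/dL or urine output below 200 mL/d.

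The variables to be gathered are narrower. Schedule footnote g gives the oxygenation ratio and then "platelets, bilirubin, hypotension/vasopressor use, GCS score, creatinine) are detailed in Section 11.1.1 and Appendix 1". Protocol 11.1.1 and Appendix 1 each open a list with "The SOFA score variables to be assessed are", and in both the only renal entry is creatinine. The urine entries in protocol Table 2 are urinalysis items such as "Leukocyte esterase"; no volume is listed.

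The table footnotes do adapt the score to other organ support and treatment: respiratory support, adrenergic agents, intubation and sedation ("For subjects who are sedated, use an estimated score for Glasgow Coma Scale"). None mentions dialysis. The planned analysis is that "SOFA score at each assessment and changes from baseline over time will be summarized using descriptive statistics".

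**The concern.** Dialysis lowers creatinine, the one renal quantity on the variable lists. A subject whose kidneys fail badly enough to need it can therefore move down the renal scale while getting worse. The urine limb would hold an anuric subject at 4, but urine output is not on the lists. If new dialysis is more common in one arm, that arm's mean SOFA is pulled in the favourable direction. The plan also treats a total score of zero as freedom from organ failure, so in the extreme a dialysed subject with no other points could receive that label.

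The situation is plausible in this population. Subjects have respiratory failure, may be ventilated, and are excluded on renal grounds only for "Evidence of kidney failure AND liver failure at screening", so kidney failure alone does not bar entry.

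**Working it through.** The documents give no sample size, effect or precision figure for SOFA, so there is no stated figure to reproduce.

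**Inputs from the documents**
- Renal thresholds (SAP Table 1, protocol Table 5): 0 if creatinine <1.2 mg/dL; 1 if 1.2-1.9; 2 if 2.0-3.4; 3 if 3.5-4.9 or urine <500 mL/d; 4 if >5.0 or urine <200 mL/d.
- Listed renal variable: creatinine only (footnote g, 11.1.1, Appendix 1).
- About 30 subjects per arm in Part 2 (SAP 3.2).

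**Assumptions, not in the documents**
- Creatinine of 5.5 mg/dL before dialysis (score 4), falling to 4.2, 2.8, 1.6 or 1.0.
- New-dialysis rates of 5% and 15%.

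**Step 1. Score one subject both ways.** The full definition takes the worse of creatinine and urine output.

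| Creatinine on dialysis | Creatinine only (change from 4) | Urine <200 mL/d | Urine 400 mL/d | Urine 1000 mL/d |
|---|---|---|---|---|
| 4.2 | 3 (-1) | 4 | 3 | 3 |
| 2.8 | 2 (-2) | 4 | 3 | 2 |
| 1.6 | 1 (-3) | 4 | 3 | 1 |
| 1.0 | 0 (-4) | 4 | 3 | 0 |

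Scored on creatinine alone, the item falls by 1 to 4 points. With urine below 200 mL/d the full definition does not move. With preserved urine output the urine limb corrects nothing, and only a dialysis rule does. There are therefore two gaps: the missing urine variable and the missing rule.

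**Step 2. Effect on change from baseline.** The loss is the gap between the two scorings, and it need not appear as a negative change. A subject with renal score 1 at baseline who worsens to 4 and is dialysed to 2 has a recorded change of 2 - 1 = +1. Held at 4, the change would be 4 - 1 = +3. Two points of worsening disappear.

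**Step 3. Effect on the arm comparison.** Let *d* be the points lost per affected subject, taken as equal in both arms, and *p* the proportion of assessed subjects newly on dialysis.
- Shift in one arm's mean = *d* x *p*.
- Between-arm bias = *d* x (*p*1 - *p*2).
- With 15% and 5%: 1 x 0.10 = 0.1; 2 x 0.10 = 0.2; 3 x 0.10 = 0.3; 4 x 0.10 = 0.4 points.
- With equal rates: *d* x 0 = 0.

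At 30 per arm those rates are 0.15 x 30 = 4.5 and 0.05 x 30 = 1.5 subjects. The bias favours the arm with more new dialysis.

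**Step 4. Does scoring on the worst value of the day prevent this?** Only in part. A higher value taken before a dialysis session on an assessment day would count. SOFA is assessed on Days 3, 5, 7, 11, 15 and at end of treatment or discharge, and on a day after dialysis has started even the worst value may already be lowered.

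**The case against.** **Urine output is within the referenced instructions.** Footnote g and 11.1.1 both send the reader to Appendix 1, whose Table 5 contains the urine limits. The SAP was written against eCRF version 6.0, which is not among the documents. A reader might infer that the oliguric scores can never be assigned. The documents do not show that, because a urine field in the eCRF cannot be ruled out. What they show is that the variable lists omit urine output. The missing dialysis rule does not depend on the eCRF.

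**A dialysis rule extends the scale.** Neither table has a renal replacement category, so its absence misapplies nothing in the published scale. That is fair. But the plan already adapts the score to other support by footnote, and dialysis directly lowers the value being scored.

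**Dialysis already present at entry may largely cancel.** Because kidney failure alone does not exclude, a reader might count such subjects as adding fully to the error. Their creatinine can be lowered both at baseline and afterwards, so much of the error may drop out of the change. The bias formula therefore uses new dialysis only.

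**The consequence is limited.** SAP 6.2.2 plans no SOFA test or model. New or worsening illness is recorded as an adverse event, and procedures are tabulated under SAP 5.5, so an excess of kidney failure could be seen elsewhere. This stands and bounds the importance of the point. It does not correct the SOFA summary itself.

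**Urine charting cannot be assumed.** Subjects on oxygen alone are eligible, nothing says their 24-hour volume is charted, and protocol 7.2 aims to limit site burden. This stands and shapes the fix.

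**Conclusion.** The point holds. The renal row and the variable lists disagree, and no rule covers renal replacement therapy. From the listed variables, a subject who starts dialysis after baseline can show a false renal improvement of usually 1-3 points. A 4-point loss needs a prior score of 4 and a worst daily creatinine below 1.2 mg/dL, so apparent full renal recovery is the extreme and not the general case.

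The between-arm bias is 0.1-0.4 points at assumed new-dialysis rates of 5% and 15%, and zero if the rates are equal. A reader might take 4 x 5% = 0.2 to 4 x 15% = 0.6 as the bias. That is the shift in one arm's mean at the maximum loss, not a difference between arms. The documents give no dialysis rate, so the size is illustrative; the wrong direction of the error does not depend on it.

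Interpretation of SOFA change and of freedom from organ failure is affected. The primary safety endpoint is not. The point merits correction because the error runs the wrong way and the remedy is cheap.

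**What to change.** 1. **SAP 6.2.2, before unblinding:** state that the renal component is scored 4 on any SOFA day with renal replacement therapy, identified from the concomitant-procedure record. Add a sensitivity summary scored on creatinine only.
2. **Variable lists and renal row:** reconcile footnote g, 11.1.1 and Appendix 1 with the tables. Use urine output where it is charted or already in the eCRF; otherwise state that the renal item is scored on creatinine plus the renal replacement rule.
3. **In the same edit:** a creatinine of exactly 5.0 mg/dL has no score in either table, and 11.1.1 assigns creatinine to the local laboratory while Appendix 1 says central. Both need reconciling.

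**Cost:** the rule is one SAP sentence plus one extra summary. The record it needs is already kept: protocol 9.5 requires procedures to be recorded, schedule footnotes i and n ask for dates and times of changes and daily recording to discharge, and SAP 5.5 summarizes them by procedure. Footnote i does not name dialysis, so completeness of those entries should be checked.

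**Downside:** a score of 4 is a convention. It can over-score a dialysed subject with preserved urine output (at 400 mL/d the urine limb gives 3). The sensitivity summary shows how much depends on it.
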